8.6. Analysis of the Secondary Efficacy Endpoints

The secondary endpoints will be analyzed in the following order of importance (high to low):

- Change from baseline in average AM and PM subject-reported 12-hour instantaneous Total Nasal Symptom Score (iTNSS) over the 14-day treatment period.
- Change from baseline in the overall Pediatric Rhinoconjunctivitis Quality of Life Questionnaire (PRQLQ) score on Day 15 (Visit 4) between treatment groups.
- Change from baseline in average AM and PM subject-reported 12-hour reflective Total Ocular Symptom Score (rTOSS) over the 14-day treatment period.

Table 5 provides an overview of the planned secondary efficacy analyses.

Table 5: Overview of Planned Secondary Efficacy

	Stats Analysis		Summary		Individual
	T	F	T	F	L
Change from Baseline in Average AM and PM 12-hour iTNSS over a 14-day Treatment Period (MMRM Approach)					
iTNSS – MMRM – FAS	Y	Y	Y		Y
iTNSS – MMRM – PPS	Y	Y	Y		
Change from Baseline in PRQLQ on Day 15 (ANCOVA model)					
PRQLQ – ANCOVA – FAS	Y	Y	Y		Y
Change from Baseline in Average AM and PM 12-hour rTOSS over a 14-day Treatment Period (MMRM Approach)					
rTOSS – MMRM - FAS	Y	Y	Y		Y
rTOSS – MMRM - PPS	Y	Y	Y		

NOTES :

- T = Table, F = Figure, L = Listing, Y = Yes display generated.
- Stats Analysis = Represents TF related to any formal statistical analyses (i.e. modeling) conducted.
- Summary = Represents TF related to summaries (i.e. descriptive statistics) of the baseline, post-treatment and change from baseline for the primary efficacy analyses method.

- Individual = Represents L related to any displays of individual subject observed raw data as well as post-baseline and change from baseline presented on the SAS dataset.

8.6.1. Analysis of Change from Baseline in iTNSS and rTOSS

The analysis of change from baseline in iTNSS and rTOSS will use both the FAS (primary) and the PPS (supportive).

Similar to the primary analysis for the primary endpoint in section 8.5.1 above, the secondary endpoints (iTNSS and rTOSS) will be evaluated using a MMRM model, adjusting for covariates that include treatment, site, baseline and study day as the within-subject effect. The interactions of site-by-treatment and baseline-by-treatment will be investigated separately in the model and will only be included in final model if they are statistically significant at the alpha=5% level. An unstructured (UN) covariance will be assumed. If the model does not converge using the unstructured covariance structure, the autoregressive (order 1) AR(1) structure will be used. If this also does not converge other covariance structures deemed appropriate to fit the data will be used. The SAS® code will be similar to the primary endpoint.

The adjusted means for each treatment and the estimated treatment differences for the treatment comparisons will be presented together with 95% confidence intervals for the differences and p-values for the treatment comparisons. The adjusted means and estimated treatment differences for the treatment comparisons will also be plotted, with corresponding 95% confidence intervals.

Descriptive statistics (number of subjects, mean, standard deviation, median, minimum and maximum) will be provided for baseline, post treatment and change from baseline by treatment group and day.

8.6.2. Analysis of Change from Baseline in the Overall PRQLQ on Day 15

The change from baseline in the overall PRQLQ at Day 15 (Visit 4) will be analyzed for the FAS using an ANCOVA model adjusting for study treatment, site, and baseline PRQLQ (linear, continuous covariate). The interactions of site-by-treatment and baseline PRQLQ-by-treatment group will be investigated separately in the ANCOVA model and will only be included in the final model if they are statistically significant at the alpha=5% level. Baseline is defined as the PRQLQ score at Day 1 (Visit 2). For subjects who withdrew early from the study the PRQLQ score at their discontinuation visit will be used, regardless of what actual study day this visit occurred on.

The statements of a SAS® PROC MIXED analysis would be:

```
proc mixed;
class treatment site;
model change = treatment site baseline;
lsmeans treatment / cl diff;
ods output lsmeans=lsmeans;
ods output diffs=diffs ;
run; quit;
```

The adjusted means for each treatment and the estimated treatment differences for the treatment comparisons will be presented together with 95% confidence intervals for the differences and p-values for the treatment comparisons. The adjusted means and estimated treatment differences for the treatment comparisons will also be plotted, with corresponding 95% confidence intervals.

Descriptive statistics (number of subjects, mean, standard deviation, median, minimum and maximum) will be provided for baseline, post treatment and change from baseline by treatment group.

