9.4. Study Drug Preparation

9.5. Administration

Each study medication bottle will contain [REDACTED] metered sprays. The study medication will be dispensed to the subjects (parents/caregivers/legal guardians, as applicable) at the study site after adequate training using a placebo NS bottle.

The subjects (with the assistance from parents/caregivers/legal guardians, as needed) will be asked to take their daily double-blind, study medication for a period of 14 days (2 weeks) following a 7 to 10 day, single-blind, placebo run-in period. The first dose (AM dose on Day 1) will be administered in the clinic at the Randomization Visit (Visit 2). The AM dose of the day of the Treatment Visit (Visit 3) will also be administered at the clinic. All other doses will be self-administered at home (with assistance from parents/guardians/caregivers, as needed). The last scheduled dose will be the PM dose on the day before the Final Visit/Discontinuation Visit (Visit 4). Study drug should not be taken (either at home or at the clinic) on the morning of the Final Visit/Discontinuation Visit (Visit 4).

Subjects will self-administer the study medication during specified study visits under the supervision of the study personnel (with assistance from parents/guardians/caregivers, as needed). Additionally, subjects will self-administer the study medication at home BID per the subject instructions provided during the single blind placebo run-in period and the treatment period (with assistance from parents/guardians/caregivers, as needed). Subjects (parents/legal guardians/caregivers, as needed) will be adequately trained in the proper use of the study medication NS bottle at the specified visits as well as reviewing the subject study medication instructions.

Detailed instructions for the proper use of the treatment NS bottles are provided in Appendix I.

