10.4. Pediatric Rhinoconjunctivitis Quality of Life Questionnaire (PRQLQ)

The PRQLQ (Appendix 3) used in this study is a validated, disease-specific, quality-of-life (QOL) questionnaire developed to measure the physical, emotional, and social impairments that are experienced by children (aged ≥ 6 to <12 years) with rhinoconjunctivitis (Juniper et al, 1998).

The PRQLQ has 23 questions in 5 domains (nose symptoms, eye symptoms, practical problems, activity limitation and other symptoms) (Juniper et al, 1998). Subjects recall how they have been during the previous week and respond to each question on a 7-point scale. The overall PRQLQ score is the mean of all 23 responses and the individual domain scores are the means of the items in those domains.

The interviewer-administered PRQLQ will be provided to subjects at the investigational site at the Randomization Visit (Visit 2) and the Final Visit/Discontinuation Visit (Visit 4). The PRQLQ administration must be the first procedure conducted at these study visits.

The study site personnel and the Investigators will be provided with detailed instructions about conducting QOL assessments in order to achieve maximum compliance with the standards of QOL assessments in a clinical study environment and to maximize data quality. Clinical staff must ask the questions exactly as worded in the questionnaire. Words should not be simplified, skipped or changed. Above all, clinical staff should never attempt to paraphrase or revise the questions. After completion of the PRQLQ, the site personnel will check the questionnaire for completeness and legibility.

An English version of the PRQLQ will be provided to all subjects who provide informed consent/assent in English. However, if a subject consents/assents in a language other than English, the PRQLQ will be provided to the subject in that language provided a validated version of the PRQLQ is available in that language. If a validated version of the PRQLQ is not available in that language, then the subject will be exempt from completing the PRQLQ.

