4.5.2. Pediatric Rhinoconjunctivitis Quality-Of-Life Questionnaire (PRQLQ)

The PRQLQ used in this study is a validated, disease-specific, quality-of-life questionnaire developed to measure the physical, emotional, and social impairments that are experienced by children (age ≥ 6 to <12 years) with rhinoconjunctivitis.³ The PRQLQ has 23 questions in 5

domains (nose symptoms, eye symptoms, practical problems, activity limitation and other symptoms). Subjects will be asked to recall their experiences during the previous week and to give their responses on a 7-point scale.

PRQLQ scores will be summarized by domains. A domain average score is calculated as the sum of the scores in that domain divided by the number of items in that domain; all items in the domain must be valid in order to calculate the corresponding average score. A domain average score will be set to missing if there is a missing item score in that domain.

The overall average PRQLQ score is calculated as the sum of the scores in all domains divided by the total number of items in the five domains; all items in the 5 domains must be valid in order to calculate the corresponding overall average score. If a domain score is missing, then the overall average PRQLQ score will be set to missing.

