8.5. Analysis of the Primary Efficacy Endpoint

8.5.1. Primary Efficacy Analysis

The primary endpoint, change from baseline in average AM and PM subject-reported 12-hour rTNSS over a 14-day treatment period, will be evaluated using a mixed-effect repeated measures (MMRM) model. The model will adjust for study treatment, site, baseline 12-hour rTNSS and study day as the within-subject effect, with the assumption that any missing data is missing at random (MAR).

The interactions of site-by-treatment and baseline-by-treatment will be investigated separately using two independent models and will only be included in the final model if they are statistically significant at the alpha=5% level. In order to determine the interaction/s to be included in the final model, the following model-fitting process will be followed:

1. The main-effects model containing study treatment, site, baseline 12-hour rTNSS and study day will be fitted first:
 - a. Unstructured covariance will initially be assumed.
 - b. If the model does not converge using the unstructured covariance structure, the autoregressive (order 1) AR(1) structure will be used.
 - c. If the AR(1) structure also does not converge, other covariance structures deemed appropriate to fit the data will be used.
2. Two independent models will be fitted using the covariance structure of the model that converged in step 1: one model containing the site-by-treatment interaction and the other model containing the baseline-by-treatment interaction. If the interaction term is significant, it will be included in the final model. If convergence is not obtained after adding both of the interaction terms (if both are significant), the more significant interaction term will be kept in the model. Any interaction term that make model not converge will not be added to the final model.

The statements of a SAS® PROC MIXED analysis would be (if the interactions of treatment*baseline and treatment*site are not statistically significant):

```
PROC MIXED;
CLASS subject treatment site day;
MODEL change = treatment site baseline day;
REPEATED day / SUBJECT = subject TYPE=UN;
LSMEANS treatment / CL DIFF E ;
ODS OUTPUT LSMEANS=lsmeans ;
ODS OUTPUT DIFFS=diffs ;
RUN ;
QUIT ;
```

The adjusted means for each treatment and the estimated treatment differences for the treatment comparisons will be presented together with 95% confidence intervals for the differences and p-

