	Change from Baseline to Day 15	n (%)	xx (xx.x)	xx (xx.x)	xx (xx.x)
		Mean (SD)	xx.x (xx.xx)	xx.x (xx.xx)	xx.x (xx.xx)
		Median	xx.x	xx.x	xx.x
		Min, Max	xx,xx	xx,xx	xx,xx
PRQLQ Domain					
Activity Limitations					
Practical Problems					
Nose Symptoms					
Eye Symptoms					
Other Symptoms					

Source: Listing 16.2.6.11

Baseline is defined as the time point "pre-dosing" at the Randomization Visit (Visit 2). Day 15 includes Visit 4 for all subjects, including those terminating early, regardless of what actual study day this visit occurred on.

SD = Standard Deviation; Max=maximum; Min=minimum; N= number of subjects in the FAS treatment group; n= number of subjects with data available

Program: xxxx.sas Executed: DDMMYYYY HH:MM

Page X of Y

Programming Note: Repeat the summary for each domain as listed in the table

Table 14.2.2.3.2 Summary of ANCOVA Analysis Results of the Overall PRQLQ Score and Individual Domains on Day 15 (Full Analysis Set)

Overall PRQLQ

Treatment Group Comparison (GSP 301 NS vs. Placebo NS)	n		LS Mean (SE)		Comparison between GSP 301 NS and Placebo NS			
	Placebo NS	GSP 301 NS	Placebo NS	GSP 301 NS	LS Mean Difference	SE of LS Mean Difference	95% CI	P-value
	xxx	xxx	xxx.x (xx.xx)	xxx.x (xx.xx)	xxx.x	xxx.xx	(xxx.x, xxx.x)	x.xxx

Source: Listing 16.2.6.11

Baseline is defined as the time point “pre-dosing” at the Randomization Visit (Visit 2). Day 15 includes Visit 4 for all subjects, including those terminating early, regardless of what actual study day this visit occurred on.

n= number of subjects with data available LS = least squares; SE = standard error

Statistical Analysis model: analysis of covariance (ANCOVA) with change from baseline as dependent variable, treatment group and site as fixed effect and baseline as covariate.

Individual statistical analysis models were made separately for each of the PRQLQ domains.

Program: xxxx.sas Executed: DDMMYY YYYY HH:MM

Page X of Y

Programming Note:

1. Repeat the analysis for each domain listed in table 14.2.2.3.1, replacing “Overall PRQLQ” with the domain name as is appropriate
2. Based on the results of the independent modeling for interactions, add the following footnotes:
 - a. If only treatment*site interaction is significant, footnote: “Site by treatment interaction is included in the model for the Overall PRQLQ analysis”.

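### Should PRQLQ scores from discontinuation visits before Day 8 be kept out of the Day 15 analysis?

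*SAP*

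**What the plan says.** Overall PRQLQ is tested third in the fixed sequence, after rTNSS and iTNSS and before rTOSS (SAP 8.4). SAP 8.6.2 specifies an ANCOVA on the FAS with treatment, site and baseline PRQLQ, baseline being the Visit 2 score. For early leavers it says: "For subjects who withdrew early from the study the PRQLQ score at their discontinuation visit will be used, regardless of what actual study day" that visit falls on. The footnotes of Tables 14.2.2.3.1 to 14.2.2.3.3 and Listing 16.2.6.11 repeat this: "Day 15 includes Visit 4 for all subjects, including those terminating early, regardless of what actual study day this visit occurred on". No earliest day is set and no PRQLQ sensitivity analysis is planned.

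On the instrument, Protocol 10.4 says: "Subjects recall how they have been during the previous week and respond to each question on a 7-point scale". It is given only at Visit 2 and Visit 4, as the first procedure. The first randomized dose follows at Visit 2, on the morning of Day 1 (Protocol 9.5), after a placebo run-in of 7 to 10 days.

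Not every leaver gives a score. Protocol 12.5 calls for the Visit 4 procedures whenever a child has to leave, but Protocol 7.4.1 ends all evaluation once consent is withdrawn. SAP 4.5.2 also requires complete questionnaires: "all items in the 5 domains must be valid in order to calculate the corresponding overall average score".

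**The concern.** A child seen on Day 2 looks back over a week made up almost entirely of run-in. The baseline score has already counted those days, so the change score partly compares the run-in with itself, yet it enters the model as a Day 15 result. FAS membership needs only one dose and one post-baseline diary assessment, so such a child can be in the analysis. If this happened often, the PRQLQ difference would be understated. Because PRQLQ gates rTOSS, a missed PRQLQ result would also end formal testing before rTOSS. With unequal withdrawal, the shift could go in either direction.

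**Working it through.** **1. The plan's own figure.** A two-sample t-test with difference 1.0, SD 3.0, two-sided alpha 5% and 90% power needs 190.1 per arm, rounded up to 191, or 382 in total. Then 382 / 0.85 = 449.4, or about 450 randomized. Both stated figures reproduce. They concern rTNSS; no PRQLQ power is stated.

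**2. Overlap.** Take the recall week as the 7 days before visit day d, with no Day 0 (SAP 6.7.2). Run-in days in that week = max(0, 8 − d): 6, 5, 4, 3, 2, 1 for Days 2 to 7, and none from Day 8. All of them are also in the baseline week. If the visit day is counted as part of the week, the counts are 5 to 0.

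**3. Loss of effect under the current rule.** Assumptions: 15% drop-out (0.15 × 450 = 67.5), visits spread evenly over Days 2 to 14, a constant daily effect from Day 1, equal withdrawal in both arms, and a share c of drop-outs giving a valid score.

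- Drop-outs among analysed scores: f = 0.15c / (0.85 + 0.15c).
- Mean run-in share over Days 2 to 14: (6+5+4+3+2+1) / 7 / 13 = 3/13.
- Shrinkage of the difference: f × 3/13.
- Early scores: 67.5 × c × 6/13, a fraction f × 6/13 of those analysed.

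**4. Power under both rules.** Start from an illustrative 90%, so the expected test statistic is 1.96 + 1.2816 = 3.2415 (rounded). Current rule: Φ(3.2415 × (1 − f × 3/13) − 1.96). Day 8 cut-off, dropping the early scores: Φ(3.2415 × √(1 − f × 6/13) − 1.96).

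| c | f | Early scores (share of analysed) | Shrinkage | Power, current rule | Power, cut-off |
|---|---|---|---|---|---|
| 0.2 | 3.41% | 6 (1.6%) | 0.8% | 89.55% | 89.54% |
| 0.5 | 8.11% | 16 (3.7%) | 1.9% | 88.89% | 88.88% |
| 1 | 15% | 31 (6.9%) | 3.5% | 87.89% | 87.85% |

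The match is not chance. Scores from Days 2 to 7 carry on average half a week of run-in, so a fraction g of them shrinks the effect by g/2. Dropping them multiplies the test statistic by √(1 − g), which is about 1 − g/2.

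**5. Other timings.** If every drop-out is seen on Days 2 to 7, shrinkage is f × 0.5 = 1.7 / 4.1 / 7.5%. If all are seen on Days 8 to 14, it is zero. The cut-off would gain power visibly only if early visits cluster at the very start. In the limit, all 15% are scored and all on Day 2, giving shrinkage of 0.15 × 6/7 = 12.9%. With an assumed standardized effect of 1/3 and 225 per arm, power then falls from 94.2% to 86.9%, against 90.3% with those scores dropped (191 per arm). No clinic visit is scheduled between Day 1 and the Visit 3 window (Days 6 to 10), so that case is remote.

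**6. Unequal withdrawal.** With 20% against 10% drop-out and a mean improvement of 0.5 to 1.0 point, bias = [0.2c/(0.8+0.2c) − 0.1c/(0.9+0.1c)] × 3/13 × (0.5 to 1.0). This gives 0.003–0.006 (c = 0.2), 0.007–0.013 (c = 0.5) and 0.012–0.023 (c = 1) point on the 0–6 scale.

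**The case for a change.** The best case for a change is that a week of run-in is not a Day 15 outcome, however conservative it may be to count it as one. Day 8 is the first day with a clean recall week. SAP 6.7.4 places Visit 4 on Days 15 to 17, and the primary MMRM leaves missing days missing under MAR. The edit would be one sentence, four footnotes and one more run, with the current rule kept as a sensitivity analysis. Early visits without withdrawal of consent are foreseeable, for instance after an adverse event or unblinding.

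The overlap stands, and Day 15 is a loose label, although the footnotes disclose it. The remedy is weaker than it looks, for two reasons.

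- **The comparison with the MMRM fails.** The MMRM keeps a drop-out's observed diary days, so its MAR assumption conditions on them. Each child has at most one post-baseline PRQLQ. Removing it leaves a complete-case ANCOVA that conditions only on treatment, site and baseline, which is a stronger assumption. Adverse events and non-adherence are listed reasons for withdrawal (Protocol 7.4), and the cut-off would in effect credit those children with the course of children who stayed. Imputation from diary scores would soften this, at the price of a further model.
- **Day 8 does not give a Day 15 estimate.** A Day 8 visit recalls Days 1 to 7; a Day 15 visit recalls Days 8 to 14. Protocol 4.2 describes a slow onset for intranasal corticosteroids, so scores from Days 8 to 14 may also fall short, and they would still count.

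**Conclusion.** This is a fair trade-off with no gain from switching. The any-day rule uses every observed score, is pre-specified and is disclosed wherever the PRQLQ is reported. Its cost is a shrinkage of about 1% to 3.5% in the PRQLQ difference, and nearer the lower end because consent withdrawal and missing items remove some leavers. With similar withdrawal in both arms the shrinkage works against the drug. With 20% against 10% drop-out, the bias is at most 0.023 point. Under an even spread of visits the cut-off leaves power unchanged to within 0.1 point. The primary endpoint and the sample size are untouched.

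These sizes rest on 15% drop-out, an even spread of visits, a constant effect from Day 1 and an unknown share of drop-outs scored; the documents support only the first. Listing 16.2.6.11 gives visit and date for each score, so the ANCOVA can be rerun without the early scores if anyone wishes to see their influence. That is optional and does not require a change to the plan.

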8.7. Efficacy Analyses of Other Endpoints of Interest

The analysis on endpoints including nasal symptoms, non-nasal symptoms, individual domains of PRQLQ and PNSS will be based on the FAS. Outputs based on the PPS will be produced only on an as needed basis for these endpoints, depending on the results from the primary and secondary endpoints.

Similar methods as described for the primary endpoint above will be applied, for the other endpoints nasal symptoms, ocular symptoms and non-nasal symptoms as listed in Section 3.2.3. Similar to the primary analysis for the primary endpoint in section 8.5.1 above, these other endpoints (nasal symptoms, non-nasal symptoms and ocular symptoms) will be evaluated using a MMRM model, adjusting for covariates treatment, site, baseline and study day as the within-subject effect. The interaction term day-by-treatment will also be included in the MMRM model for the by-day analysis for rTNSS and iTNSS. The individual symptom analysis will be conducted by including a 'by individual symptom' statement to the proc mixed model. An unstructured (UN) covariance will be assumed. If the model does not converge using the UN covariance structure, the autoregressive-order 1 (AR(1)) structure will be used. If this also does not converge other covariance structures deemed appropriate to fit the data will be used. The SAS® code will be similar to the primary endpoint. If there is no convergence for the MMRM model with day-by-treatment term, ANCOVA model will be used to present the by-day estimates for rTNSS and iTNSS.

Similar to the analysis for the secondary endpoint in Section 8.6.2 above, the other endpoints overall PNSS and individual domains PNSS, PRQLQ will be evaluated using an analysis of covariance (ANCOVA) model adjusting for covariates that include treatment, site and baseline. The individual domain analysis will be conducted by including a 'by individual domain' statement to the proc mixed model.

The adjusted means for each treatment and the estimated treatment differences for the treatment comparisons will be presented together with 95% confidence intervals for the differences and p-values for the treatment comparisons. For some of the endpoints the adjusted means and estimated treatment differences for the treatment comparisons will also be plotted, with corresponding 95% confidence intervals. For the by-day analysis, the above will be presented for each day. For the individual symptom/domain analysis, the above will be presented for each symptom/domain.

Descriptive statistics (number of subjects, mean, standard deviation, median, minimum and maximum) will be provided for baseline, post treatment and change from baseline by treatment group (and by day for certain endpoints) for each endpoint detailed above.

